in the 9-12 month window post-⁶⁸Ga-PSMA-HBED-CC scan. Follow up imaging will only be performed on subjects that have positive ⁶⁸Ga-PSMA-HBED-CC findings because conventional imaging assessment for disease is primarily targeting suspicious lesions identified by ⁶⁸Ga-PSMA-HBED-CC PET/CT. Interpretation of follow-up imaging will be performed by local read. Preferably, the follow-up conventional imaging should be the same modality/modalities as the initial staging work-up to allow for reproducible and accurate comparisons. Conventional imaging standards as described below will be used to determine tissue positive for prostate cancer disease. Conventional imaging will not be used to determine negative prostate cancer disease regions due to its inherently low negative predictive value.

Tissue positive for prostate cancer disease based on follow-up imaging:

12.2.2.1. Lymph nodes will be assessed by change in size.

i. Positive for disease:

- a. -For subjects undergoing systemic treatment (alone or in combination with targeted treatment): If on post-treatment follow-up imaging within 3-12 months, visually suspicious lymph nodes seen on CT or MRI decrease by more than 30% in short axis diameter and PSA declines by more than 50%.
 - If PSA increases by more than 25% (PCWG3 definition of recurrence) on systemic therapy, then an increase in the size of lesion by more than 20% in the short axis diameter will be considered a positive for disease.
- b. In subjects with localized suspected lymph node(s) receiving targeted treatment without concomitant systemic treatment there are two ways to achieve positive for disease designation:
 - If the subject shows a decrease of PSA by greater than 50% after targeted treatment and the lymph node does not enlarge (change in size less than 20% in the short axis diameter or less than 3 mm increase in short axis diameter) [OR]
 - If on post-treatment follow-up imaging within 3-12 months, lymph nodes seen on CT or MRI decrease by more than 30% in short axis diameter (with a minimum of 3 mm in change in size)
- c. For untreated subjects: If on follow-up imaging within 3-12 months, lymph nodes seen on CT or MRI increase by more than 20% in short axis diameter (with a minimum of 3 mm in change in size).

ii. Negative for disease:

- Conventional Imaging follow-up will not be used for assessment of negativity for disease.

iii. Indeterminate for disease

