- Regions with no lymph nodes determined to be positive by the conventional imaging criteria described above and without pathology will be designated regions indeterminate for prostate cancer disease.
- Subjects that have had neither pathology sampling, nor conventional imaging follow up will have all regions designated as indeterminate for disease by reference standard.

12.2.2.2. Visceral lesions (non-lymph node soft tissue or organ) and prostate bed and prostate lesions will be assessed by change in size.

i. Positive for disease:

- a. For subjects undergoing systemic treatment (alone or in combination with targeted treatment): If on post-treatment follow-up imaging within 3-12 months, visually conspicuous lesions seen on CT or MRI decrease by more than 30% in long axis diameter and PSA declines by more than 50%.
 - If PSA increases by more than 25% (PCWG3 definition of recurrence) on systemic therapy, then an increase in the size of lesion by more than 20% in the long axis diameter will be considered positive for disease.
- b. In subjects with localized suspected lesions(s) receiving targeted treatment without concomitant systemic treatment there are two ways to meet positive disease criteria:
 - If the subject demonstrates a decrease of PSA by greater than 50% after targeted treatment [*OR*]
 - If on post-treatment follow-up imaging within 3-12 months, lesions seen on CT or MRI decrease by more than 30% in long axis diameter (with a minimum of 3 mm in change in size)
- c. For untreated subjects: If on follow-up imaging within 3-12 months, lesions seen on CT or MRI increase by more than 20%

in long axis diameter (with a minimum of 3 mm in change in size).

ii. Negative for disease:

- Conventional Imaging follow up will not be used for assessment of negativity for disease

iii. Indeterminate for disease

- Regions with no visceral lesions determined to be positive by the conventional imaging criteria described above and without pathology will be designated as visceral regions indeterminate for prostate cancer disease.
- Prostate bed and prostate regions not determined to be positive by the conventional imaging criteria described above and without pathology will be designated as prostate regions indeterminate for prostate cancer disease.
- Subjects that have had neither pathology sampling, nor conventional imaging follow up will have all prostate and visceral regions designated as indeterminate for disease by reference standard.

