13.3. Definitions of ^{68}Ga PSMA-HBED-CC accuracy

13.3.1. True positive definitions

13.3.1.1. **^{68}Ga PSMA-HBED-CC PET/CT positive for nodal metastases by internal blind reader** – and pathology (if available) positive for that node, or node positive for disease by imaging as defined in Section 12.2.2.1 If this criteria is met, the subject is defined as true positive for nodal disease.

13.3.1.2. **^{68}Ga PSMA-HBED-CC PET/CT positive for visceral metastases by internal blind reader** – and pathology (if available) positive for that visceral lesion, or, visceral lesion positive for disease by imaging as defined in Section 12.2.2.2. If this criteria is met, the subject is defined as true positive for visceral disease.

13.3.1.3. **^{68}Ga PSMA-HBED-CC PET/CT positive for osseous**

metastases by internal blind reader - and pathology (if available) positive for that osseous lesion, or, osseous lesion positive for disease by imaging as defined in Section 12.2.2.3. If this criteria is met, the subject is defined as true positive for osseous disease.

13.3.1.4. A single nodal, visceral, or osseous region determined as true positive as defined above is sufficient to define the subject as true positive by ⁶⁸Ga PSMA-HBED-CC PET/CT.

13.3.2. **True negative definitions**

13.3.2.1. **⁶⁸Ga PSMA-HBED-CC PET/CT negative for nodal metastases by internal blind reader** – and pathology (if available) negative for disease, and, extra-pelvic node not positive for disease by imaging. If this criteria is met, the subject is defined as true negative for nodal disease.

13.3.2.2. **⁶⁸Ga PSMA-HBED-CC PET/CT negative for visceral metastases by internal blind reader** – and pathology (if available) negative for disease, and, visceral lesion not positive for disease by imaging. If this criteria is met, the subject is defined as true negative for visceral disease.

13.3.2.3. **⁶⁸Ga PSMA-HBED-CC PET/CT negative for osseous metastases by internal blind reader** - and pathology (if available) negative for disease, and, osseous lesion not positive for disease by imaging. If this criteria is met, the subject is defined as true negative for osseous disease.

13.3.3. **False positive definitions:**

13.3.3.1. **⁶⁸Ga PSMA-HBED-CC PET/CT positive for nodal metastases by internal blind reader**, pathology (if available) is negative, and imaging demonstrates that node is not positive for disease. If this criteria is met, the subject is defined as false positive for nodal disease.

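### After targeted-only treatment, imaging can confirm a node or soft-tissue lesion only by response; one that grows while PSA rises is left indeterminate

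*Combined protocol and SAP*

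**What the plan says.** Section 12.2.2 sets the imaging reference standard for use when pathology is not available, and splits it by the treatment given after PET.

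- **Systemic treatment (12.2.2.1 i.a).** A node is positive if it shrinks by more than 30% and PSA falls by more than 50%. If PSA instead rises by more than 25%, "then an increase in the size of lesion by more than 20% in the short axis diameter will be considered a positive for disease".
- **Targeted treatment only (12.2.2.1 i.b).** "In subjects with localized suspected lymph node(s) receiving targeted treatment without concomitant systemic treatment there are two ways to achieve positive for disease designation". The first is "If the subject shows a decrease of PSA by greater than 50% after targeted treatment and the lymph node does not enlarge", where not enlarging means a change under 20% or an increase under 3 mm. The second is that "lymph nodes seen on CT or MRI decrease by more than 30% in short axis diameter", with a 3 mm minimum.
- **Untreated (12.2.2.1 i.c).** A node is positive if "lymph nodes seen on CT or MRI increase by more than 20% in short axis diameter", with a 3 mm minimum.

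Section 12.2.2.2 repeats the three branches for visceral, prostate and prostate-bed lesions, using the long axis. In its branch b "there are two ways to meet positive disease criteria": a PSA fall above 50%, with no condition on size, or shrinkage above 30% with a 3 mm minimum.

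A region that meets no imaging criterion and has no pathology is indeterminate (12.2.2.1 iii, 12.2.2.2 iii). Section 13.3.5 makes regions and subjects with insufficient data non-evaluable.

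**The concern.** The plan accepts growth as evidence of disease in the branches on either side of i.b, but not in i.b itself, and gives no reason. Branch c is limited to untreated subjects and branch a to systemically treated ones, so neither rule can be borrowed. The same change in size and PSA is thus labelled differently because of treatment alone.

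The lesions lost are PET-positive ones that progress, which would count as true positives in either neighbouring branch. Losing them lowers both the primary endpoint (per-subject sensitivity) and the secondary one (PPV). Section 5.4.6 sends the local PET result to the treating clinician, so the index scan may influence who enters this branch. Section 13.1 intends the results to inform the target sensitivity of a larger study, so a label that depends on treatment could carry forward.

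**Working it through.** **1. The plan's own figure.** Section 13.1 gives 95% half-widths for N = 30. At 80%: 1.96 × √(0.80 × 0.20/30) = 14.3%, as printed. The other four rows also reproduce (16.4, 15.5, 12.8 and 10.7%). The point does not depend on these figures; they give a scale for the effect.

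**2. The rules applied to one lesion.** Take growth from 8 to 12 mm: (12 − 8)/8 = +50%, and +4 mm.

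| PSA change | Systemic (a) | Targeted only (b), node | Targeted only (b), soft tissue or prostate bed | Untreated (c) |
|---|---|---|---|---|
| +30% or +100% | positive | not positive | not positive | positive |
| 0% | not positive | not positive | not positive | positive |
| −60% | not positive | not positive | positive (PSA route) | positive |

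Branch b is out of line with both neighbours only in the first row, growth with a PSA rise above 25%. At a flat PSA it agrees with branch a. At −60% the soft-tissue lesion is already positive.

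**3. The resulting label.** Without pathology the region is indeterminate under Section 12. One other true-positive region still makes the subject true positive (13.3.1.4). Failing that, the subject is non-evaluable. He is not a false negative, because 13.3.4.4 requires PET to be negative in all regions.

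**4. Size, by assumption.** The documents do not say how many subjects would be affected. Assume 25 evaluable PET-positive subjects, of whom 21 are true positive when the progressing man is counted: 21/25 = 84.0%.

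- Non-evaluable, as Section 12 and 13.3.5 imply: (21 − 1)/(25 − 1) = 20/24 = 83.3%, a loss of 0.7 points.
- False positive, only if 13.3.3 is read that way: 20/25 = 80.0%, a loss of 4.0 points.

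For sensitivity, assume 24/30 = 80.0% (Wilson 62.7 to 90.5%). With k such men dropped, the estimate is (24 − k)/(30 − k):

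- k = 1: 23/29 = 79.3%
- k = 3: 21/27 = 77.8% (59.2 to 89.4%)
- k = 5: 19/25 = 76.0% (56.6 to 88.5%)

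**5. The rule proposed under the fix (PSA rise above 25%, growth above 20% and at least 3 mm).** The 8 to 12 mm lesion becomes positive in branch b at PSA +30% or +100%. The 0% and −60% rows do not change.

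**The case against.** A reader might infer four stronger things that the documents do not support.

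- **That a progressing lesion can never be confirmed.** Pathology is the primary standard and a positive result overrides imaging. The rescue is uncertain: 12.2.1 makes pathology available within 60 days of PET, 6.4.4 collects it to 12 months, and growth is judged at 3 to 12 months. The two pathology windows need reconciling. For soft tissue, a PSA fall above 50% is enough even if the lesion grows.
- **That the lesion becomes a false positive.** Section 13.3.3.1 scores one when pathology, if available, is negative and "imaging demonstrates that node is not positive for disease". Read without pathology, that would catch this node. But 12.2.2 says conventional imaging will not establish negativity. That conflict is separate and affects every branch.
- **That a PET-positive node outside the treated field is necessarily caught.** The plan does not say whether targeted and untreated are judged per subject or per lesion. Judged per lesion, such a node falls under branch c and its growth counts.
- **That any growth should count in i.b.** The first node route makes enlargement disqualifying when PSA falls by more than 50%. Growth regardless of PSA would empty that condition, and would be looser than branch a, which requires a PSA rise.

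It is also fair to object that the affected group is narrow, that this is a 30-subject pilot without significance testing, and that indeterminate is the plan's chosen label for unresolved cases. A subject who later starts systemic treatment might move to branch a, though the plan is silent on switching. These points limit how often the gap matters. None explains why growth with a PSA rise counts in branches a and c but not in b.

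**Conclusion.** The gap is real and narrow. In both i.b lists, growth with a PSA rise after targeted-only treatment is not confirmable by imaging. Without usable pathology or another true-positive region, the subject drops out of sensitivity and PPV as non-evaluable. Bone is outside the point, because a new bone lesion counts whatever the treatment.

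The effect is likely small: 0.7 points of PPV per man under the assumed 21/25, well inside the planned half-widths of 10.7 to 16.4 points. Both the base counts and the number of men are assumptions. The 80.0% figure needs the separate conflict with 13.3.3 to be resolved against Section 12. The point merits a correction because the label depends on treatment and the remedy is cheap; it does not put the pilot in doubt.

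**What to change.** This changes outcome classification only.

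1. Add a third route to 12.2.2.1 i.b and 12.2.2.2 i.b: the lesion is positive for disease if PSA rises by more than 25% and, on imaging at 3 to 12 months, it grows by more than 20% with a minimum of 3 mm. Use the short axis for nodes and the long axis for visceral, prostate and prostate-bed lesions. This mirrors branch a and keeps the 3 mm minimum used elsewhere in i.b and in i.c. The PSA condition preserves the rule that an enlarging node with a PSA fall is not positive.
2. State that targeted and untreated are judged per lesion, so that a lesion outside the treated field is assigned consistently.

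The cost is one bullet in each of two sections and one sentence on assignment, with no new scans or data. The downside is a slight departure from any reference-standard definition shared with other sites, which 13.1 envisages for pooling. Reporting the results under i.b as it now stands as well deals with that. Make the change before reference-standard classification, so that it cannot be seen as chosen after the results.

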5.4. PET/CT scan

- 5.4.1. **Scan coverage.** Scan coverage will extend from mid-thigh to the base of the skull, starting from the mid-thighs to minimize urinary bladder radiotracer accumulation at the start of PET imaging. Subject to void immediately prior to imaging.
- 5.4.2. **Bed position.** Scan time will be dependent on scanner capabilities. At a minimum, 3 minutes per bed position will be used.
- 5.4.3. **Discharge.** Subject must be monitored for adverse events for a minimum of 2 hours post-injection.
- 5.4.4. **Local Analysis.** A board-certified nuclear medicine physician on-site will interpret the images within 3 business days of the imaging study. These interpretations will not be used for final evaluation, however regional positivity results will be collected as study data.
- 5.4.5. **Internal Blinded Reads.** Imaging data will be interpreted by two different readers in a random order at separate reading sessions. Cross sectional imaging from the CT will be available for anatomic correlate. Final reads for each subject will be interpreted as positive or negative for the presence of pelvic nodal disease, and positive or negative for the presence of osseous metastatic disease and soft tissue metastases outside of the pelvis. All readers will have undergone ⁶⁸Ga PSMA PET training.
- 5.4.6. **Results dissemination.** Local analysis will be shared with the subject's

clinician and will be included in the subject's medical record.

5.5. **Visual Interpretation of PET data (internal blind reads)**

Regions of suspected disease will be graded on a two-point scale by each reader (0=Negative or 1=Positive). A region will be judged as positive if at least one lesion in this region is visually positive. Regions are defined in Table 12.1 in Section 12. Criteria for visual interpretation positive for disease are detailed in Section 12.1.1.

5.6. **Follow-up imaging**

All subjects should be followed as per standard of care consistent with the institution/physician. Reports and copies of any conventional imaging obtained during the 12 month window following the PSMA-HBED-CC PET/CT scan will be obtained. Clinical notes will also be reviewed to identify metastatic lesions. Interpretation of follow-up imaging is performed by local institution following standard procedures. Preferable comparison imaging would be the same imaging device as the initial re-staging work-up as per RECIST guidelines.

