Blinded Read Logistics: Imaging data will be de-identified. PET data will be interpreted by two different readers in a random order at separate reading sessions. Cross sectional imaging (CT or MRI) from the ^{68}Ga -PSMA-HBED-CC PET will be available for anatomic correlate. The blinded readers will be blinded to all other imaging results and all other clinical data.

Reader Positivity and Negativity Definition: Sub-regions defined in Table 12.2 will be graded for the presence of suspected disease on a two-point scale by each reader (0=Negative or 1=Positive). A region will be judged as positive if at least one lesion in this region is visually positive..

12.1.1. Criteria for visual interpretation:

Sub-regions of suspected disease will be graded on a two-point scale by each blinded reader (0=Negative or 1= Positive). A region will be judged as positive if at least one lesion in this region is visually positive.

12.1.1.1. Lymph nodes will be considered positive if the ^{68}Ga -PSMA-HBED-CC uptake is focal and greater than blood pool (adjacent or mediastinal blood pool).

- Lymph nodes will be classified further by region: pelvic, retroperitoneal, thoracic and other. Additionally, pelvic lymph nodes will be sub-classified according to their localization as follows: R/L obturator, R/L external iliac, R/L internal iliac and other (total of 7 subgroups). These pelvic sub-regions will be correlated with reference standard results in these sub-regions, however this sub-region data will not be directly used for evaluation of the primary or secondary endpoints, but for exploratory analysis.

12.1.1.2. Visceral lesions will be considered positive if the ^{68}Ga -PSMA-HBED-CC uptake is focal and greater than physiologic background activity of the involvement organ or anatomic site.

- Visceral lesions will be classified further by major organ: lung, liver, pancreas... as defined in Table 2. These sub-regions will be correlated with reference standard results in these sub-regions, however this sub-region data will not be directly used for evaluation of the primary or secondary endpoints, but for exploratory analysis.

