12.1.1.3. Bone lesions will be considered positive if the ^{68}Ga -PSMA-

HBED-CC uptake is focal and greater than physiologic bone marrow.

- Bone lesions will be classified by further by region: spine, ribs, pelvis, extremities, skull, sternum, and clavicle, as Defined in Table 12.2. These sub-regions will be correlated with reference standard results in these sub-regions, however this sub-region data will not be directly used for evaluation of the primary or secondary endpoints, but for exploratory analysis.

12.1.1.4. Prostate bed and prostate lesions will be considered positive if the ⁶⁸Ga-PSMA-HBED-CC uptake is focal and greater than physiologic background activity of the involvement organ or anatomic site.

12.2. Reference standard definition:

12.2.1. Histopathology/Biopsy will be the primary determinate of tissue positivity and negativity for prostate cancer disease. Pathology date, organ, and location as well as any notes related to the pathology will be obtained from the subject chart. The anatomical region/sub-region the pathology occurred in will be assigned by the investigator team:

⁶⁸Ga-PSMA-HBED-CC positive findings are aimed to be confirmed by histopathology/biopsy if clinically feasible. Pathology performed 60 days before or after the ⁶⁸Ga-PSMA-HBED-CC PET will be available for correlation.

Histopathological procedures and biopsies will be performed as clinically indicated and as per institutional protocol.

12.2.1.1. Lymph Nodes, Visceral Lesions, and Bone Lesions positive for disease by pathology.

- Lesions with positive pathologic confirmation will be regarded as positive for disease. The regionality of the resected tissue will be assigned into respective regions and sub-regions as described above in Table 12.2.

12.2.1.2. Lymph Nodes and Visceral Lesions negative for disease by pathology.

- Tissue removed and negative for pathology are considered negative for prostate cancer disease, unless subsequent conventional imaging or ⁶⁸Ga-PSMA-HBED-CC PET imaging demonstrates that targeted tissue were not resected. In this case:

- i. Subjects can be rescanned with dedicated CT, MRI, or ⁶⁸Ga-PSMA-HBED-CC PET/CT to determine if the suspicious ⁶⁸Ga-PSMA-HBED-CC tissue was removed. If the tissue is confirmed as removed, this is considered negative for disease.

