ii. If ^{68}Ga -PSMA-HBED-CC PET/CT positive tissue is still present, a needle biopsy can be pursued at the discretion of the treating physician. Images of the procedure will be reviewed to determine if the correct tissue was biopsied.

- If the ^{68}Ga -PSMA-HBED-CC PET/CT positive tissue was biopsied, a negative pathologic finding of the biopsied tissue is considered negative for disease.
- If the ^{68}Ga -PSMA-HBED-CC PET/CT positive tissue was biopsied, a positive pathologic finding of the biopsied tissue is considered positive for disease.
- If biopsy or re-biopsy is not performed, or the wrong tissue was biopsied, change in node size as measured by conventional imaging and as defined below will be the criteria by which disease status will be defined.

12.2.1.3. Bone lesions: Given the high rate of false negative biopsies for osseous metastases in subjects with prostate cancer, subjects with negative bone biopsies of ^{68}Ga -PSMA-HBED-CC PET positive lesions will be further evaluated:

- If pathology demonstrates an alternative diagnoses that is known to be ^{68}Ga -PSMA-HBED-CC positive (eg Renal Cell Carcinoma metastases, Paget's disease), then this will be considered negative for disease.
- If pathology is indeterminate, then follow-up imaging as described below will be performed as per clinical standards at the site.

12.2.1.4. Although not routinely performed during standard practice, immunohistochemical staining for PSMA of tumor specimens (primary and lymph node metastases) may be performed, although not required.

12.2.1.5. All regions not sampled for biopsy/histopathology will be designated as indeterminate for disease by pathology. Conventional imaging follow-up may be used in these cases to determine tissue status.

12.2.2. Follow-up Imaging will be used as a secondary assessment for prostate cancer in the event pathology information is not available:

All subjects will be tracked for follow-up conventional imaging between 3-12 months post ^{68}Ga -PSMA-HBED-CC (dedicated CT, MRI and/or bone scan) as per site standard of care. If no follow-up imaging has been performed within the 9 months following the ^{68}Ga -PSMA-HBED-CC scan, then the research study will pay for an additional follow-up CT scan to be performed

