12.2.2.3. Bone lesions will be considered:

i. Positive for disease on baseline assessment:

- Any positive sclerotic lesion on the CT portion of the ⁶⁸Ga-PSMA-HBED-CC PET or on a separate CT obtained \leq 30 days before or after the PET/CT.
- Focal uptake on the baseline bone scan performed within one month of ⁶⁸Ga-PSMA-HBED-CC PET.
- Any MRI lesion in bone read as positive on the initial MRI performed within one month of ⁶⁸Ga-PSMA-HBED-CC PET.

ii. Positive for disease on follow up:

- Any new positive sclerotic lesion on CT within 12 months of ⁶⁸Ga-PSMA-HBED-CC PET scan
- Any new MRI bone lesion within 12 months of ⁶⁸Ga-PSMA-HBED-CC PET scan
- Any new focal uptake in bone within 12 months of ⁶⁸Ga-PSMA-HBED-CC PET scan

- In subjects with localized suspected bone lesion(s) receiving targeted treatment without concomitant systemic treatment:
- If the subject demonstrates a decrease of PSA by greater than 50% after targeted treatment.

iii. Negative for disease:

- Conventional Imaging follow up will not be used for assessment of negativity for disease

iv. Indeterminate for disease:

- Regions with no bone lesions determined to be positive by the conventional imaging criteria described above and without pathology will be designated bone regions indeterminate for prostate cancer disease.

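### Sclerosis on the index PET/CT's own CT can, alone, confirm bone disease, so index test and reference standard are not independent for Region 4

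*Combined protocol and SAP*

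**What the plan says.** - **Reference standard for bone (12.2.2.3(i)).** Under the label "Positive for disease on baseline assessment", bone is reference-positive on "Any positive sclerotic lesion on the CT portion of the" index PET. A separate CT within 30 days, a bone scan within one month and an MRI within one month are alternatives. None is required in addition.
- **Rank of imaging (12.2.2).** Imaging comes after pathology: "Follow-up Imaging will be used as a secondary assessment for prostate cancer in the event pathology information is not available".
- **What the blinded readers see (5.4.5, 12.1).** "Cross sectional imaging from the CT will be available for anatomic correlate". Everything else is masked: "The blinded readers will be blinded to all other imaging results and all other clinical data".
- **Index rule for bone (12.1.1.3).** A lesion is called positive if "HBED-CC uptake is focal and greater than physiologic bone marrow". Sclerosis is not a criterion.
- **Route to the endpoint (13.3.1.3, 13.3.1.4).** A reader-positive bone finding is a true positive if pathology supports it, or if there is an "osseous lesion positive for disease by imaging as defined in Section 12.2.2.3". For the subject, "A single nodal, visceral, or osseous region determined as true positive as defined above is sufficient".
- **Endpoint wording (13.1, 13.2).** Section 13.1 says that evaluating sensitivity requires pathology, follow-up conventional imaging or both. Section 13.2 describes confirmation by pathology and conventional imaging follow-up.

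**The concern.** The index test is a PET/CT read with its CT visible. For bone, that CT may also supply the whole reference result. The only non-PET information the readers have can therefore also verify their call. A reader who sees sclerosis may call adjacent uptake more readily, and the same sclerosis then confirms the call. This is the structure of incorporation bias. No section says who reads the index CT for the reference standard, or whether that person is blind to the PET.

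The overlap is specific to bone. The node, visceral and prostate-bed criteria need a size change or a PSA response after the scan. Through 13.3.1.4, however, one bone region can decide a subject's status on the primary endpoint. Section 13.1 says the estimate will help set the target sensitivity for a larger study, and names the reference standard as a source of uncertainty. With 30 subjects, a few reclassifications move the result.

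**Working it through.** **1. Trace the rule.** Sclerosis on the index CT, no pathology: bone reference-positive (12.2.2.3(i)). Reader also calls uptake in that lesion: osseous true positive (13.3.1.3). One such region: subject true positive (13.3.1.4). No other examination enters the chain.

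**2. Compare with the rest of the plan.** A same-day CT is not follow-up, so step 1 does not meet 13.1 or 13.2. Section 12.2.2.1(iii) makes all regions indeterminate when a subject has neither pathology nor follow-up imaging, but 12.2.2.3(i) would make the same subject's bone region positive.

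**3. Direction for PPV = TP/(TP + FP).** For a PET-positive bone region the rule can add a true positive. It adds no false positive, because conventional imaging is not used to establish negativity (12.2.2, 12.2.2.3(iii)). It can therefore only support or raise PPV.

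**4. Direction for sensitivity = TP/(TP + FN).** Under 13.3.4.3, sclerosis without uptake makes the subject false negative for osseous disease. Under 13.3.4.4 the subject is a false negative overall if every region is PET-negative. The rule can then add to both terms of the denominator. Section 5.6 instead restricts false negatives to positive biopsies, in which case the rule adds only true positives. The two sections disagree, so the net direction is open.

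**5. The plan's own figures.** The half-widths in 13.1 are 1.96 × √(p(1 − p)/30). For p = 70, 75, 80, 85 and 90% this gives 16.40, 15.49, 14.31, 12.78 and 10.74 points, which match the printed 16.4, 15.5, 14.3, 12.8 and 10.7. They do not depend on the reference standard, so this point leaves them unchanged.

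**6. Illustration for sensitivity.** The documents give no number of subjects confirmed only by the index CT, so the counts are assumed. Start from 24 TP and 6 FN among 30 subjects (80.0%; 13.1 anticipates more than 80%). Let k subjects rest only on the index CT and become non-evaluable when it is set aside. The denominator is TP + FN; 13.1 prints TP + FP, which is the PPV formula. Intervals are Wilson, as 13.2 specifies: centre (p + z²/2n)/(1 + z²/n), half-width z√(p(1 − p)/n + z²/4n²)/(1 + z²/n), z = 1.96.

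| k | k true positives removed | k false negatives removed |
|---|---|---|
| 0 | 24/30 = 80.0% (62.7 to 90.5) | 24/30 = 80.0% (62.7 to 90.5) |
| 2 | 22/28 = 78.6% (60.5 to 89.8) | 24/28 = 85.7% (68.5 to 94.3) |
| 4 | 20/26 = 76.9% (57.9 to 89.0) | 24/26 = 92.3% (75.9 to 97.9) |
| 10 | 14/20 = 70.0% (48.1 to 85.5) | not possible (only 6 FN) |

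**7. Illustration for Region 4 PPV.** Assume 10 bone true positives and no false positives, with 4 resting only on the index CT. Without pathology or another positive imaging criterion, those 4 are indeterminate (12.2.2.3(iv)) and so non-evaluable (13.3.5.1). PPV goes from 10/10 to 6/6. At p = 1 the Wilson lower bound is n/(n + z²): 10/13.84 = 72.2% and 6/9.84 = 61.0%.

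**The case against.** The best defence is that confirmation needs two different signals: tracer uptake called by the reader, and sclerosis on CT. The formal index rule is uptake above marrow, with the CT only an anatomic aid. Uptake without sclerosis is not confirmed by this rule. Pathology takes precedence, the overlap concerns one of four regions, and this is a pilot without significance testing. Section 13.1 could also be read as excluding a subject whose only support is the index CT.

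Most of this stands as a limit on reach, and it rules out saying that the scan simply confirms itself. It does not remove the overlap. The bone call is a visual yes/no judgement made with the CT in view, and 13.3.1.3 refers to 12.2.2.3 without excluding its baseline route. No passage shows or sizes an influence of sclerosis on the readers, so that step remains plausible rather than demonstrated.

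Two stronger inferences are tempting and not supported:
- **That the rule inflates sensitivity as well as PPV.** Follow-up imaging is planned only for PET-positive subjects (12.2.2), so baseline imaging is one of the few ways a PET-negative subject can become a false negative. Setting the index CT aside could raise sensitivity.
- **That the illustrative PPV could fall to 6/10.** That counts the four unsupported regions as false positives. Only a literal reading of 13.3.3.5 without pathology would do so, against 12.2.2.3(iii) and (iv).

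**Conclusion.** The point holds as a lack of independence, not as a demonstrated inflation. For Region 4, and for subjects whose only confirmed region is bone, one acquisition can supply part of the index test and the entire reference result. That route also conflicts with 13.1 and 13.2. PPV can only be supported or raised by it; for sensitivity the net direction is not established while 5.6 and 13.3.4 disagree.

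The size cannot be computed from the documents. Under the assumed counts, four index-CT-only subjects move sensitivity from 80.0% to 76.9% or to 92.3%, depending on whether they are true positives or false negatives. In the PPV example the point estimate does not change; what weakens is the evidence behind it. These figures assume that regions without other support become non-evaluable, and that the affected subjects have no other region deciding their status. This is a worthwhile, inexpensive improvement rather than a flaw that invalidates the pilot.

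**What to change.** 1. Record the source of each bone reference-positive: pathology, index CT, separate CT, bone scan, MRI, new lesion on follow-up, or PSA response.
2. Report per-subject sensitivity, per-subject PPV and Region 4 PPV twice: as planned, and with bone regions supported only by the index CT treated as non-evaluable. Apply this to true positives and false negatives alike, and re-derive subject status under 13.3.
3. Keep a region in the second analysis if it is supported by pathology, a separate CT within 30 days, a bone scan or MRI within one month, or the PSA-response criterion.
4. Reconcile 12.2.2.3(i) with the wording of 13.1 and 13.2, and 5.6 with 13.3.4, before the data are analysed.

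The cost is one data field and one extra analysis, with no scans or readers added. The second estimate will have fewer evaluable regions and subjects, and the loss is selective. Section 12.2.2.3(ii) counts only new lesions on follow-up imaging, so a lesion already sclerotic on the index CT will rarely be kept in by later scans, and section 6.1 collects baseline bone scan, MRI and CT only if they were performed. Overtly sclerotic disease will tend to drop out, so the second estimate should be read beside the first and not in place of it.
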